#### **4.3 Assessment Windows**

Data will be summarized by nominal study visit recorded in the database.

#### **4.4 Handling of Dropouts or Missing Data**

Missing data will be treated as missing and no method for imputation is planned for study population or safety analyses except for the partial end dates/times for concomitant medications (Section 5.6) and partial onset dates/times for AEs (Section 7.2.1). When applicable, missing data for binary and selected continuous efficacy endpoints will be imputed using a most conservative/worst case approach, and the related details are described in Section 6.

Time to event endpoints will have events coded as right censored or competing events per the

following table:

**Table 1 Missing Data and Competing Events Coding for Time to Event Data Analyses**

Endpoint	Right Censoring and Competing Events
Subject Survival	Subjects who are still alive as of the last known follow-up will be right censored as of the date of last subject contact when the subject was known to be alive.
Time to actual ICU Discharge or Medical Equivalence of ICU Discharge (if different from actual ICU discharge date)	Subjects who did not discharge or medical equivalence of discharge from the ICU at any time during follow-up will be right censored as of the date of last subject contact when the subject was known to be in the ICU. Subject death will be considered a competing event. Competing risk methods e.g., cumulative incidence function (CIF) will be used to account for competing events in the analysis.
Time to actual Hospital Discharge or Medical Equivalence of Hospital Discharge (if different from actual hospital discharge date)	Subjects who did not discharge or medical equivalence of discharge from the hospital at any time during follow-up will be right censored as of the date of last subject contact when the subject was known to be in the hospital. Subject death will be considered a competing event. Competing risk methods e.g., cumulative incidence function (CIF) will be used to account for competing events in the analysis.
Time to Clinical Response	Subjects who did not experience clinical response or died at any time during follow-up will be right censored as of the date of last non-missing assessment of NEWS on or prior to Day 29.

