9 STATISTICS

9.1 Statistical Methods

Descriptive statistics will include the number of non-missing observations, mean, standard deviation (SD), median, minimum, and maximum values for the continuous/quantitative data or absolute and relative frequency counts and percentages for categorical/qualitative data. All statistical tests will be 2-sided at a significance level of 0.05.

An interim analysis will be conducted after 50 subjects (approximately 25 per group) for safety variables through Day 29. Due to the exploratory nature of this phase 2 study, the multiplicity adjustments will not be considered; full details will be described in the statistical analysis plan. This interim evaluation simply represents Sponsor safety due diligence.

There will be 3 analysis populations in this study; 2 populations for efficacy assessments and 1 population for safety evaluation.

The intention to treat (ITT) population is defined as all subjects who are randomized. The ITT population will be used for all efficacy analyses.

The Per-Protocol (PP) population is defined as the subset of subjects included in the ITT population who do not present major protocol violations which might have an impact on the primary efficacy endpoint, and complete at least 80% of the IP. The primary efficacy analyses will be carried out using the PP population if different from the ITT population.

The Safety population is defined as the subset of subjects who receive at least any amount of IVIG plus SMT or SMT alone. Safety analyses will be based on the Safety population.

The primary efficacy analysis will be carried out on the ITT population and repeated on the PP population (if different from the ITT population) by Fisher's exact test or Chi-square test. Secondary and exploratory efficacy analyses will be analyzed by means of Kaplan-Meier survival estimates and curves and compared between treatment groups by means of the Log-rank test for time to event variables, analysis of covariance (ANCOVA) or Student's t test for normally-distributed variables or Wilcoxon rank-sum test for non-normally-distributed variables. Detailed data handling and evaluation procedures and details of the interim reviews will be described in the Statistical Analysis Plan (SAP). The SAP may include exploratory analyses of various aspects of SMT inclusive of different interventional strategies and evolving treatment modalities.

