#### 4.6 Data Derivations and Transformations

The following derivations will be used in this study:

Study Day:

- Date of assessment – date of randomization + 1 for assessments done on or after date of randomization
- Date of assessment – date of randomization for assessments done before date of randomization

Baseline Observation: the last non-missing value prior to randomization.

Duration:

- Duration in days = end date – start date + 1
- Duration in minutes = end time in minutes – start time in minutes

Origin or Start Date for Time to Event Endpoints:

- Time to death: date of randomization
- Time to ICU Discharge (actual and medical equivalence, if applicable): date of randomization or date of ICU admission, whichever was later
- Time to Hospital Discharge (actual and medical equivalence, if applicable): date of randomization
- Time to Clinical Response: date of randomization

Event Date for Time to Clinical Response:

- If a subject met the criteria for clinical response at multiple assessments, the date of the first assessment meeting the definition of clinical response will be used as the event date for deriving time to clinical response.

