## 6.2 Secondary Efficacy Endpoints and Analyses

### Time to ICU discharge (Actual and Medical Equivalence)

Time to actual ICU discharge is defined as duration of actual ICU stay from Day 1 through Day 29 that is recorded on the eCRF All Visits page "General Duration of Hospitalization, & Overall Requirement for Mechanical Ventilation, ICU Admission and/or Oxygen Supplementation". The proportion of subjects who are discharged from the ICU will be estimated using the CIF. Deaths that occur prior to discharge from the ICU will be treated as a competing risk. The estimated cumulative incidence and associated two-sided 95% CI on Days 15 and 29 will be displayed. Test for equality of the CIF between treatment groups will be conducted using Gray's test.

Additionally, medical equivalence of ICU discharge date will be recorded on the eCRF if it is different from the actual ICU discharge date, and the time to medical equivalence of ICU discharge will be analyzed using the same method as described above. The proportion of subjects who are medical equivalence of discharge from the ICU will be estimated using the CIF. Deaths that occur prior to medical equivalence of ICU discharge will be treated as a competing risk. The estimated cumulative incidence and associated two-sided 95% CI on Days 15 and 29 will be displayed. Test for equality of the CIF between treatment groups will be conducted using Gray's test.

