### **Time to hospital discharge (Actual and Medical Equivalence)**

Time to actual hospital discharge is defined as duration of hospitalization from Day 1 through Day 29 that is recorded on eCRF All Visits page “General Duration of Hospitalization, & Overall Requirement for Mechanical Ventilation, ICU Admission and/or Oxygen Supplementation”. The proportion of subjects who are discharged from the hospital will be estimated using the CIF. Deaths that occur prior to discharge from the hospital will be treated as a competing risk. The estimated cumulative incidence and associated two-sided 95% CI on Days 15 and 29 will be displayed. Test for equality of the CIF between treatment groups will be conducted using Gray’s test.

Additionally, medical equivalence of hospital discharge date will be recorded on the eCRF if it is

different from the actual hospital discharge date, and the time to medical equivalence of hospital discharge will be analyzed using the same method as described above. The proportion of subjects who are medical equivalence of discharge from the hospital will be estimated using the CIF. Deaths that occur prior to medical equivalence of hospital discharge will be treated as a competing risk. The estimated cumulative incidence and associated two-sided 95% CI on Days 15 and 29 will be displayed. Test for equality of the CIF between treatment groups will be conducted using Gray's test.

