### **Time to clinical response**

Clinical response is defined as the NEWS score <=2 maintained for 24 hours from Day 1 through Day 29. The time to the first occurrence of clinical response will be estimated using the Kaplan-Meier (KM) method. The KM estimates along with 95% CI, and survival curves will be provided. Based on the KM estimates, the probabilities of achieving first clinical response and associated 95% CIs on Days 15 and 29 will be reported; in addition, the 25th, 50th (median), and 75th percentiles of the time to first clinical response with associated 95% CIs will be provided, as data permit. The survival rates between treatment groups will be compared using Log-rank test. The p-value from Log-rank test will be presented.

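### Time to clinical response censors deaths in a Kaplan-Meier analysis, so the reported response probabilities come out too high and the percentile times too short

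*SAP*

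**What the plan says.** SAP Table 1 (section 4.4) sets out censoring and competing events for each time-to-event endpoint. The row for clinical response reads: "Subjects who did not experience clinical response or died at any time during follow-up will be right censored". The censoring date is the last non-missing NEWS on or before Day 29, and no competing event is coded. SAP 6.2 (Time to clinical response) applies Kaplan-Meier and the log-rank test. From the Kaplan-Meier curve, "the probabilities of achieving first clinical response and associated 95% CIs on Days 15 and 29 will be reported", and the 25th, 50th and 75th "percentiles of the time to first clinical response with associated 95% CIs will be provided, as data permit".

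The two discharge rows of the same table say: "Subject death will be considered a competing event". SAP 6.2 carries this through for the ICU ("Deaths that occur prior to discharge from the ICU will be treated as a competing risk") and for the hospital ("Deaths that occur prior to discharge from the hospital will be treated as a competing risk"), with the CIF and Gray's test in both cases.

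Protocol 9.1 names "Kaplan-Meier survival estimates and curves and compared between treatment groups by means of the Log-rank test for time to event variables" and mentions no competing-risk method. SAP 4.6 says that if the response criteria are met at several assessments, "the date of the first assessment meeting the definition of clinical response will be used as the event date".

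**The concern.** Censoring removes a dead subject from the risk set and lets that subject's future be represented by the survivors, as though response were still possible. The resulting curve describes a hypothetical setting in which nobody dies. SAP 6.2 does not label it that way; it presents the output as the probability of achieving response by Day 15 and Day 29. In an ICU population where death is the primary endpoint, the two quantities can differ materially.

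Two things are at stake. First, the level: each arm's response probability is overstated and each percentile time reached is too early. Second, the contrast: at the same response hazard the overstatement is larger in the arm with more deaths. If the treatment prevents deaths, part of the gain in the true probability of responding disappears from the reported figures.

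The wording has a smaller fault. Taken literally, its reference to death at any time would censor a responder who dies later, which conflicts with the event-date rule in SAP 4.6.

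**Working it through.** **No planned figure to reproduce.** Protocol 9.2 and SAP section 9 give no power, effect size, death rate or response rate. The only Day 29 mortality in the protocol background (8.0% against 11.6%) comes from a remdesivir trial in hospitalized patients, not from this ICU population. All rates below are assumptions.

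**Direction, by a small example.** Take 50 subjects: 5 respond on Day 5, 5 die on Day 8, 3 respond on Day 12, 7 respond on Day 14, 5 die on Day 20, 7 respond on Day 22, and 18 are alive without response at Day 29.

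- Day 15: responders 15/50 = 30.0%. Kaplan-Meier with deaths censored: 1 − (45/50)(37/40)(30/37) = 1 − 0.675 = 32.5%.
- Day 29: responders 22/50 = 44.0%. Kaplan-Meier: 1 − 0.675 × (18/25) = 1 − 0.486 = 51.4%.

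**Size, under constant hazards.** Let r be the true probability of response by Day 29 and d the probability of death before response by Day 29, over 28 days from randomization. The response hazard is a = [r/(r+d)] × [−ln(1−r−d)]/28, and the death hazard b has d in place of r in the first factor. Then:

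- CIF(t) = [a/(a+b)] × [1 − exp(−(a+b)t)], which equals r at t = 28
- 1 − KM(t) = 1 − exp(−at), so at Day 29 it is 1 − (1−r−d)^(r/(r+d))

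For r = 0.50 and d = 0.30: 1 − 0.20^(0.625) = 0.634, an overstatement of 13.4 points.

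| Death before response (d) | Day 29, 1 − KM, r = 30% | Day 29, 1 − KM, r = 50% | Overstatement at Day 29 (points) | Overstatement at Day 15 (points) |
|---|---|---|---|---|
| 10% | 31.8% | 53.4% | 1.8 to 3.4 | 0.5 to 1.1 |
| 20% | 34.0% | 57.7% | 4.0 to 7.7 | 1.2 to 2.6 |
| 30% | 36.8% | 63.4% | 6.8 to 13.4 | 2.1 to 5.0 |
| 40% | 40.3% | 72.2% | 10.3 to 22.2 | 3.4 to 9.3 |

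**Median.** The Kaplan-Meier median is ln 2/a. At r = 0.50 the CIF reaches 50% at 28 days by construction. Kaplan-Meier gives 25.4 days at d = 0.10 (a = 0.0273) and 19.3 days at d = 0.30 (a = 0.0359). At r = 0.30 neither method reaches a median by Day 29.

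**Timing of deaths.** At r = 0.50 and d = 0.30, 1 − KM is 50% if every death follows the last response, and r/(1−d) = 0.50/0.70 = 71.4% if every death precedes the first response.

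**Between arms.** Halve the death hazard in one arm and leave the response hazard unchanged. Since 1 − KM depends only on a, it cannot differ between arms.

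| Control arm (r, d) | True response, control | True response, death hazard halved | 1 − KM, both arms |
|---|---|---|---|
| 40%, 20% | 40.0% | 42.7% | 45.7% |
| 45%, 40% | 45.0% | 53.0% | 63.4% |

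**At this sample size.** In a simulation of 50 subjects per arm with daily assessment (4,000 runs, r = 50%), mean Day 29 estimates from Kaplan-Meier against the CIF were 53.3% against 50.0% at 10% mortality, 57.4% against 49.9% at 20%, and 62.9% against 49.9% at 30%. Kaplan-Meier was the higher in 99.3% to 100% of runs.

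**The case against.** Kaplan-Meier with log-rank is what Protocol 9.1 names, and the log-rank test remains a valid comparison of cause-specific response hazards. Both statements are true. But the SAP already left that protocol wording for discharge because of death, and the same reason applies here. A valid log-rank test also does not make the reported probabilities correct.

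The size rests wholly on assumption. With one fixed r and d, the timing of deaths alone moves the overstatement from 0 to 21 points. At about 50 per arm, the 95% half-width for a proportion near 50% is about 1.96 × √(0.25/50) = 14 points, so the smaller errors lie within sampling noise. Percentiles are given only where the data allow, and at 30% response no median would be reported. This stands as a limit on the size. It does not excuse a bias with a known sign that can be removed at almost no cost.

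The hidden difference requires an effect on death with none on response, and the primary analysis would look for such an effect directly. It is under 3 points in the milder example. That is fair, although reducing mortality is the trial's primary objective, so the case is not remote.

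The literal-wording problem is minor: SAP 4.6 and the first-occurrence language in 6.2 together suggest that a later death does not undo a response. It is still worth tidying.

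Finally, the SOFA and NEWS repeated-measures models also give no rule for death. That is a separate matter; the point made here concerns only deaths censored in a Kaplan-Meier analysis.

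**Conclusion.** The concern holds. Followed as written, the SAP would report as probabilities of response figures that are never below the true ones, and that exceed them as soon as one response follows a death without response. Percentile times are affected in the opposite direction. No other part of the SAP restores deaths as non-responders for this endpoint, and the treatment of death is inconsistent with the discharge rows of the same table.

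The direction needs no assumption about rates. The size does: under constant hazards with 30% to 50% truly responding, the Day 29 error runs from about 2 points at 10% death to about 22 points at 40% death. This should be fixed, in proportion: it is one secondary endpoint in an exploratory pilot. Deaths are counted in the primary analysis and handled as competing events for discharge, and death is a category of the ordinal scale.

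**What to change.** In Table 1, code death before first response as a competing event. Right-censor only subjects alive without response, at their last NEWS on or before Day 29. State that a responder who later dies keeps the event at first response, in line with SAP 4.6.

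In SAP 6.2, report the CIF of response by arm with 95% CIs at Days 15 and 29, take percentiles from the CIF where they are reached, and compare arms with Gray's test as for discharge. Correcting the estimates strictly requires only the CIF; Gray's test brings the comparison into line with the discharge endpoints. The log-rank test can stay as a supplement, labelled as a comparison of cause-specific response hazards.

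The cost is one table row and one paragraph. The methods are already specified in the SAP, and no new data are needed.

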#### 4.5 Multiple Comparisons

Because of the exploratory nature of this study, there will be no adjustment for multiple comparisons.

#### 4.6 Data Derivations and Transformations

The following derivations will be used in this study:

Study Day:

- Date of assessment – date of randomization + 1 for assessments done on or after date of randomization
- Date of assessment – date of randomization for assessments done before date of randomization

Baseline Observation: the last non-missing value prior to randomization.

Duration:

- Duration in days = end date – start date + 1
- Duration in minutes = end time in minutes – start time in minutes

Origin or Start Date for Time to Event Endpoints:

- Time to death: date of randomization
- Time to ICU Discharge (actual and medical equivalence, if applicable): date of randomization or date of ICU admission, whichever was later
- Time to Hospital Discharge (actual and medical equivalence, if applicable): date of randomization
- Time to Clinical Response: date of randomization

Event Date for Time to Clinical Response:

- If a subject met the criteria for clinical response at multiple assessments, the date of the first assessment meeting the definition of clinical response will be used as the event date for deriving time to clinical response.

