5 SELECTION AND WITHDRAWAL OF SUBJECTS

5.1 Inclusion Criteria

A subject must meet all the following inclusion criteria to be eligible for participation in this study:

1. Hospitalized male or female subjects of ≥ 18 years of age at time of Screening who are being treated in the ICU for COVID-19 for not longer than 48 hours or for whom a decision has been made that COVID-19 disease severity warrants ICU admission.
2. Has laboratory-confirmed novel coronavirus (SARS-CoV-2) infection as determined by qualitative PCR (reverse transcriptase [RT]-PCR), or other FDA-approved-or regulatory-

GRIFOLS Bioscience Industrial Group	Number	BLG-CL-PRT-000020	Version	4.0	Status	Effective	Effective Date	19-Jul-2021	41 of 91
	GC2007 - A Multicenter, Randomized, Open-label Parallel Group Pilot Study to Evaluate Safety and Efficacy of High Dose Intravenous Immune Globulin (IVIG) plus Standard Medical Treatment (SMT) versus SMT alone in						Page		

authority-approved diagnostic assay for COVID-19 in any specimen during the current hospital admission prior to randomization.

3. Illness (symptoms of COVID-19 of any duration requiring ICU level care), and the following:
 - a) Radiographic infiltrates by imaging (chest X-Ray, CT scan, etc.), AND
 - b) Requiring mechanical ventilation and/or supplemental oxygen.

Note: ICU level care is defined as the medical need for intensive or invasive monitoring; immediate or impending need for supportive care of the airway, breathing, or circulation; and/or stabilization of acute severe or life-threatening complications of COVID-19.
4. Any one of the following related to COVID-19: i. Ferritin > 400ng/mL, ii. LDH > 300 U/L, iii. D-Dimers > reference range, or iv. C-reactive protein (CRP) > 40 mg/L.
5. Subject provides informed consent prior to initiation of any study procedures.

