## 6. EFFICACY ANALYSES

All efficacy analyses will be carried out using the ITT population. Data on all efficacy endpoints will be listed and tabulated if appropriate.

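### Time to ICU discharge is clocked from ICU admission when that follows randomisation, and the SAP does not say how subjects never admitted to the ICU are handled

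*SAP*

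**What the plan says.** SAP 4.6 gives the start date for this endpoint as "Time to ICU Discharge (actual and medical equivalence, if applicable): date of randomization or date of ICU admission, whichever was later". The neighbouring entry reads "Time to Hospital Discharge (actual and medical equivalence, if applicable): date of randomization", and time to death and time to clinical response also start at randomisation. Study Day in the same section is the assessment date minus "date of randomization + 1 for assessments done on or after date of randomization", so the day of randomisation is Day 1.

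SAP 6.2 says "Time to actual ICU discharge is defined as duration of actual ICU stay from Day 1 through Day 29", and SAP 2.2.2 and Protocol 4.1.2 define the endpoint over the same interval. Cumulative incidence is reported at Days 15 and 29, arms are compared by Gray's test, and "Deaths that occur prior to discharge from the ICU will be treated as a competing risk".

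Protocol 5.1, criterion 1, admits subjects already in the ICU for up to 48 hours and also those "for whom a decision has been made that COVID-19 disease severity warrants ICU admission".

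SAP Table 1 has subjects without ICU discharge "right censored as of the date of last subject contact when the subject was known to be in the ICU". SAP 6 states "All efficacy analyses will be carried out using the ITT population", which SAP 4.2 defines as everyone randomised. SAP 6.2 assigns zero days to subjects never ventilated and to those never on oxygen. Neither of its ICU sections has a matching rule for subjects never admitted.

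**The concern.** This is the only time-to-event endpoint whose start can depend on something that happens after randomisation. If treatment changes when, or whether, a subject enters the ICU, it changes the clock and possibly who is counted. The comparison would then no longer be purely between randomised groups. A subject who avoids the ICU has done well, yet nothing in the SAP turns that into an event. If IVIG averted admissions, losing those subjects would hide the benefit.

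**Working it through.** **1. The two definitions compared.** Take a hypothetical subject randomised on Study Day 1, admitted to the ICU on Study Day 4 and discharged from it on Study Day 12. Use the SAP 4.6 duration formula, end − start + 1.

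- Clock from Day 1 (SAP 2.2.2, 6.2): 12 − 1 + 1 = 12 days.
- Clock from admission (SAP 4.6): 12 − 4 + 1 = 9 days.
- If still in the ICU on Study Day 29: 29 days on the Day 1 clock, but 29 − 4 + 1 = 26 on the SAP 4.6 clock.

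On the SAP 4.6 clock, the Day 15 and Day 29 estimates are days since randomisation for some subjects and days since admission for others. Late-admitted subjects have less than 29 days of follow-up on that scale.

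**2. Subjects never admitted, case by case.**

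- Alive, actual discharge: no admission date, no discharge date, and no last contact in the ICU for Table 1 to use.
- Died: Table 1 names death as a competing event without qualification. The death can be counted if the start defaults to randomisation.
- Medical equivalence: a recorded date can be counted on the same condition.

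**3. Size.** There is no planned figure to reproduce: SAP 9 gives about 100 subjects with no event rate, effect size or power. From the documents: 1:1 allocation, so 50 per arm, and a two-sided 5% level. Everything else is assumed:

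- q = share not yet in the ICU at randomisation;
- a = share of those never admitted;
- 60% of admitted subjects in each arm leave the ICU alive by Day 29;
- every never-admitted subject survives.

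Expected number never admitted per arm = 50 × q × a. Proportion out of the ICU among all randomised = f + (1 − f) × 0.60, where f = q × a. For q = 30%:

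- SMT (a = 10%): 50 × 0.3 × 0.1 = 1.5 subjects; 0.03 + 0.97 × 0.60 = 61.2%.
- IVIG (a = 60%): 50 × 0.3 × 0.6 = 9 subjects; 0.18 + 0.82 × 0.60 = 67.2%.

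| q | a, SMT v IVIG | Never admitted, SMT v IVIG | Left of 100 | Admitted only | All randomised |
|---|---|---|---|---|---|
| 10% | 10% v 40% | 0.5 v 2 | 97.5 | 60% v 60% | 60.4% v 61.6% |
| 30% | 10% v 40% | 1.5 v 6 | 92.5 | 60% v 60% | 61.2% v 64.8% |
| 50% | 10% v 40% | 2.5 v 10 | 87.5 | 60% v 60% | 62.0% v 68.0% |
| 10% | 10% v 60% | 0.5 v 3 | 96.5 | 60% v 60% | 60.4% v 62.4% |
| 30% | 10% v 60% | 1.5 v 9 | 89.5 | 60% v 60% | 61.2% v 67.2% |
| 50% | 10% v 60% | 2.5 v 15 | 82.5 | 60% v 60% | 62.0% v 72.0% |

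**4. Effect on the test.** Each scenario was simulated with 2000 trials, using a log-rank test that keeps deaths in the risk set (equivalent to Gray's test under complete follow-up). Deaths were 35% in both arms, and the study day of ICU discharge followed the same distribution in both. The fix was modelled as a start at randomisation, with never-admitted subjects counted as out of the ICU at time 0. Simulation error near 5% is about √(0.05 × 0.95 / 2000) = 0.5 points.

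| Scenario | Rejection, SAP 4.6 clock, never-admitted left out | Rejection, fix |
|---|---|---|
| Equal non-admission (q = 30%, a = 20% in both; 6 lost) | 5.0% | 4.8% |
| All admitted, 3-day delay under IVIG, q = 30% | 5.6% | 5.6% |
| All admitted, 3-day delay under IVIG, q = 50% | 5.9% | 5.8% |
| Non-admission 10% v 60%, q = 30% | 5.2% | 18.0% |
| Non-admission 10% v 60%, q = 50% | 5.7% | 40.0% |

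The 3-day delay shortens that arm's mean clock by q × 3 = 0.9 days (q = 30%) or 1.5 days (q = 50%), with little effect on the test.

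**The case against.** A reader might infer that the SAP drops never-admitted subjects and discards deaths before admission. The documents do not support that. No passage excludes anyone, the analysis is declared ITT, and Table 1 counts death as a competing event without requiring admission. With no admission date, the Day 1 rule can be read as leaving randomisation as the only possible start. The accurate description is that handling is undefined. The real gap is the surviving, never-admitted subject.

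A reader might also infer that moving the clock materially distorts the test. In the scenarios above it did not.

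The later start is arguably faithful to the word stay, since waiting outside the ICU is not ICU time. That has some force, but SAP 6.2 already analyses duration of ICU stay separately, and the time-to-event endpoint is itself defined from Day 1.

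Never-admitted subjects may be few: criterion 3 requires illness needing ICU-level care, plus ventilation or oxygen. The documents give no count either way. The strong asymmetry in the last scenarios is assumed, and with equal non-admission the test stays near 5%.

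Finally, calling every never-admitted subject out of the ICU from Day 1 would clash with counting their deaths. For medical equivalence it would contradict eligibility, because every subject needs ICU-level care at entry. This objection stands, and the fix separates these cases.

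**Conclusion.** The point holds as an internal contradiction and a gap. SAP 4.6 states a rule that, for late-admitted subjects, makes the start a post-randomisation event, gives a different time from SAP 2.2.2 and 6.2, and mixes time scales at Days 15 and 29. How never-admitted subjects enter is undefined, and survivors among them are likely to be lost.

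The size cannot be fixed from the documents. The clock shift alone moved rejection by less than 1 point. Leaving out never-admitted subjects removed 2 (q = 10%, a = 20% in both arms: 2 × 50 × 0.1 × 0.2) to 17.5 of 100, and it mattered mainly when non-admission differed by arm. These results assume that admitted subjects fare alike in both arms. If the subjects kept out of the ICU were the milder ones, the admitted remainder of that arm would be sicker and the comparison could turn against it.

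This is worth correcting before analysis, but it is a secondary endpoint in a pilot without multiplicity adjustment. The primary mortality analysis is unaffected.

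**What to change.** In SAP 4.6, set the start to the date of randomisation for all subjects, for both actual and medical-equivalence ICU discharge. In Table 1 and SAP 6.2:

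- Count any death before ICU discharge, including one before or without admission, as the competing event on its date.
- For actual discharge, give subjects alive at Day 29 and never admitted zero ICU days (event at the start), in line with the ventilation and oxygen rules.
- For medical equivalence, use the recorded date on which ICU-level care was no longer required.
- Reword the censoring rule so that a subject lost before Day 29 has a date whether or not they were in the ICU.

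The cost is one line in SAP 4.6 and a few in Table 1 and 6.2. Randomisation, ICU admission and ICU discharge dates are already collected. SAP 6.2 records the medical-equivalence date only when it differs from actual discharge, so a completion note should make clear that it is also needed for subjects never admitted.

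There are two downsides. Time waiting for admission counts in the clock for late-admitted subjects, and the zero-day event uses knowledge, gained later, that admission never occurred.
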